5.2 Exclusion Criteria

An individual who meets any of the following criteria will be excluded from participation in this study:

- Pregnancy (negative pregnancy test required for women of child-bearing age)
- Currently on a platelet inhibitor (such as clopidogrel) other than aspirin or NSAIDS, or on a blood thinner (such as heparin, enoxaparin, or a novel oral anticoagulant), which is unable to be held for planned bronchoscopy
- INR \geq 1.5 (after correction and only if checked pre-operatively based on clinical indication)
- Platelets ≤ 100,000 (after correction)
- Absence of tissue diagnosis of non-small cell lung cancer either prior to procedure or during onsite pathology review at time of bronchoscopy in patients without the above specified high-risk features

CONFIDENTIAL

• Absolute contraindication to bronchoscopy

5.3 Vulnerable Subjects

Vulnerable subjects will not be included in this study.

5.4 Inclusion of Men and Women

Men and women of any races and ethnic groups are eligible for this trial.

5.5 Strategies for Recruitment and Retention

Participants will be recruited from outpatient interventional pulmonary clinic visits and from the inpatient setting at NYU Langone Medical Center. Potential participants will be identified based on referrals to the interventional pulmonary team for a diagnostic and/or therapeutic bronchoscopy. Patients who have been identified as being eligible to participate in this study will be approached in the inpatient setting, in the Ambulatory Surgery/Endoscopy unit or during interventional pulmonary clinic visits.

We expect to recruit women and minorities. The number of women and minorities recruited will be dependent on the demographics of the lung cancer population at NYULMC. Our recruitment plan will not include the use of any NYULMC media services or recruitment material.

5.5.1 Use of DataCore/Epic Information for Recruitment Purposes

This study will utilize EPIC to identify subjects. Any recruitment information sent by email will utilize Send Safe email.

Once potential subjects have been identified, the study team will notify the treating physician (TP) that they have patients eligible to participate as follows:

- Provide TP with names of potential subjects, and discuss directly with TP whether or not enrollment of particular patients would be appropriate
- Only if TP agrees that particular patient would be appropriate for this study, potential subjects will be directly contacted during office clinic visit, on the Ambulatory Sugery/Endoscopy unit, or inpatient hospital stay

Once contact is made, approved recruitment language will be used to communicate the reason they are being contacted and subjects will be asked if they are interested in participating in this specific study. Should the potential subjects agree, the study team will provide the subjects with information regarding the next steps for participation.

If a subject requests information regarding opting out of further recruitment for all research, subjects will be directed to contact [contact] or [name].

5.6 Duration of Study Participation

The total duration of study participation is 14 days. BCI will be performed at time of standard of care bronchoscopy on day 0. Peripheral blood will be collected by the investigatory team prior to BCI on the day of procedure, which will be drawn off the intravenous catheter inserted for the standard of care bronchoscopy to avoid a separate blood draw whenever possible. The investigatory team will also collect blood samples at approximately 7 days and 14 days after BCI (± 3 days). During each blood

draw, the volume of blood collected will be approximately 2 teaspoons (10 ml). This will occur at routine standard of care follow up clinic visits whenever possible. Alternatively, the investigatory team will collect blood samples at approximately 7 days and 14 days after BCI at the Perlmutter Cancer Center.

Total Number of Participants and Sites

- Total number of participants: 15-24
- Sites: New York University Langone Medical Center

5.7 Participant Withdrawal or Termination

5.7.1 Reasons for Withdrawal or Termination

Participants are free to withdraw from participation in the study at any time upon request. An investigator may terminate participation in the study if:

- Any clinical adverse event (AE), laboratory abnormality, or other medical condition or situation
 occurs such that continued participation in the study would not be in the best interest of the
 participant
- The participant meets an exclusion criterion (either newly developed or not previously recognized) that precludes further study participation

5.7.2 Handling of Participant Withdrawals or Termination

If participant withdraws after treatment with BCI, the participant will be contacted via phone to monitor for any adverse events during the seven day period post-BCI. If participant withdraws after post-BCI blood draws have been performed, then their samples will be discarded.

If participant misses follow up appointment for blood draws on day 7 and 14 post-BCI, the participant will be contacted via phone. If participant does not respond to three phone calls, the participant will be considered lost to follow up.

5.8 Premature Termination or Suspension of Study

This study may be temporarily suspended or prematurely terminated if there is sufficient reasonable cause. Written notification, documenting the reason for study suspension or termination, will be provided by the suspending or terminating party regulatory authorities. If the study is prematurely terminated or suspended, the PI will promptly inform the IRB and will provide the reason(s) for the termination or suspension.

Circumstances that may warrant termination or suspension include, but are not limited to:

- Determination of unexpected, significant, or unacceptable risk to participants
- Demonstration of efficacy that would warrant stopping
- Insufficient compliance with protocol requirements
- Data that are not sufficiently complete and/or evaluable
- Determination of futility

Study may resume once concerns about safety, protocol compliance, data quality are addressed and satisfy the IRB.

6 Procedural Intervention

6.1 Description of BCI

6.1.1 Administration of BCI

This will be an open label, phase I pilot study without a control group. As described in Section 2.2, the Flexible ERBECRYO[™] Probe of 1.9mm outer diameter (ERBE, Inc., Tubingen, Germany) will be advanced through a bronchoscope to reach the target peripheral tumor, alternatively the ERBECRYO[™] 2 single-use flexible 1.1mm outer diameter cryoprobe will be used if robotic bronchoscopy is being performed. The flexible cryoprobe, which reaches a minimum reported temperature of -89°C, will be applied to the target tumor. Freeze time will be administered based on a dose escalation protocol, as described below. The freeze phase will be followed by a passive thaw phase, which will occur until the flexible cryoprobe has separated from the target tissue. The total number of freeze-thaw cycles will be performed (depending on tumor size) from distal to proximal within the target tumor. For each one centimeter of the longest diameter, one freeze-thaw cycle will be performed. The flexible cryoprobe will only be inserted into one airway to facilitate the cryoablation. Providers will be instructed to remain greater than 2 cm away from critical structures. The objective will not be to completely engulf the peripheral tumor in an ice ball, but to cryoablate a portion of the peripheral tumor.

We will evaluate for formation of an "ice ball" with fluoroscopy as well as via bronchoscopic visualization (when feasible) as we perform BCI. We will note the presence or absence of discernible ice ball formation for each patient at each dose level after completion of the BCI procedure.

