| Brief Summary | This is a first-in-human, safety and feasibility study of bronchoscopic cryo- immunotherapy (BCI) of peripheral lung tumors in advanced non-small cell lung cancer (NSCLC) and suspected NSCLC. BCI has the potential to stimulate anti-tumor immune responses. Pre- and post-BCI peripheral blood samples will be analyzed to assess for anti-tumor immune responses. Post- BCI peripheral blood will be collected 7 and 14 days after the procedure. Additionally, pre-BCI bronchoalveolar lavage (BAL) specimens will be collected to correlate PD-1 phenotype on pre-BCI BAL lymphocytes by single cell RNA sequencing and BCI-induced anti-tumor immune responses. | | |
| Phase | Phase I | | |
| Objectives Primary: • Establish safety and feasibility of BCI and determine the maximu tolerated dose (MTD) (i.e., freeze duration) Secondary: | | | |
| Assess the extent of BCI-induced anti-tumor immune respons | | | |
| Methodology Dose-escalation trial using a 3+3 design Primary: Feasibility and Safety | | | |
| | Feasibility: successful performance of BCI in at least 80% of participants in whom BCI is attempted Safety endpoints: Dose-limiting toxicity (DLT), defined as incidence of bleeding complications and pneumothorax, length of time to perform BCI, length of fluoroscopy exposure during BCI, and other adverse events | | |
| Endpoints | Secondary: Immune Analysis and Tumor Response Changes in peripheral blood CD8⁺ T cells expressing a combination of Ki67⁺,PD-1+, HLA-DR⁺, CD38⁺, and Bcl-2^{low} after BCI Changes in peripheral blood lymphocyte gene expression after BCI, which will be assessed by the PanCancer OncolmmuneTM profile panel, a 770-plex gene expression panel covering innate and adaptive immune responses (NanoString® Technology, Seattle, WA) Correlation of PD-1 phenotype of pre-BCI BAL lymphocytes by single-cell RNA sequencing and BCI-induced anti-tumor immune responses. | | |
| Study Duration 12 months | | | |
| Participant Duration | 14 days | | |
| Duration of IP administration | BCI will be performed once at the time of a standard-of-care bronchoscopy for another indication. BCI is anticipated to take approximately 15-25 minutes. | | |

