The Flexible ERBECRYO[™] Probe of 1.9mm outer diameter (ERBE, Inc., Tubingen, Germany) will then be inserted through the guide sheath or the ERBECRYO[™]2 single-use flexible 1.1mm outer diameter cryoprobe through the robotic bronchoscope and advanced to reach the peripheral tumor. The cryoprobe will be applied to the target tumor. The cryoprobe will be maintained and calibrated based on manufacturer standards. In this study, freeze time will be selected based on a dose escalation protocol (Please see Section 2.2.3 for further details.) The freeze phase will be followed by a passive thaw phase, which will last until the flexible cryoprobe has separated from the target tissue. Freese-thaw cycles will be performed (with exact number based on tumor size and dose escalation protocol) from distal to proximal within the target tumor. One freeze-thaw cycle will be performed per one cm diameter of the tumor. Only one airway will be used to access the target tumor. Providers will be instructed to remain greater than 2 cm away from critical structures. The objective will not be to completely engulf the peripheral tumor in an "ice ball", but to cryoablate a portion of the peripheral tumor.

We will evaluate for formation of an ice ball with fluoroscopy as we perform BCI. We will note the presence or absence of discernible ice ball formation for each patient at each dose level after completion of BCI.

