2.2.3 BCI Dose Rationale

BCI of peripheral lung tumors has not been performed previously. To maximize safety, the initial freeze time is shorter than standard freeze times for cryobiopsy of peripheral lesions (15). Our dose escalation will initiate patients at a safe freeze time for which there is extensive clinical experience with related procedures. If there is no complication from this, in the next cohort of patients we will gradually escalate dose to those higher than are routinely performed in bronchoscopic cryobiopsy.

CONFIDENTIAL

Freeze times will be escalated up to 30 seconds based on tolerability. In comparison, freeze times of up to 20 minutes have been safely administered during percutaneous cryoablation of peripheral lung tumors (7, 10). Although an optimal freeze time duration is unknown, longer freeze times may be needed in order to induce anti-tumor immune responses. Based on tolerability, freeze times will be increased as described in the following table:

| Dose Level | Freeze Time (per site) | Thaw Time |
|------------|------------------------|---|
| Level 1 | 1 second | Will last until the probe separates from target |
| | | tissue* |
| Level 2 | 2 seconds | Will last until the probe separates from target |
| | | tissue* |
| Level 3 | 3 seconds | Will last until the probe separates from target |
| | | tissue* |
| Level 4 | 5 seconds | Will last until the probe separates from target |
| | | tissue* |
| Level 5 | 10 seconds | Will last until the probe separates from target |
| | | tissue* |
| Level 6 | 20 seconds | Will last until the probe separates from target |
| | | tissue* |
| Level 7 | 30 seconds | Will last until the probe separates from target |
| | | tissue* |

* Thaw times at each dose level will be captured for each site.

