4.2.3 Sub-Set Analysis and Exploratory Endpoints

- Investigation of changes in peripheral blood CD8⁺ T cells displaying a combination of Ki67⁺, PD-1+, HLA-DR⁺, CD38⁺, and Bcl-2^{low} after BCI at each dose level. This sub-set analysis will investigate if there is an optimal freeze time duration for inducing anti-tumor immune responses.
- 2) Investigation of changes in peripheral blood CD8⁺ T cells displaying a combination of Ki67⁺,PD-1+, HLA-DR⁺, CD38⁺, and Bcl-2^{low} after BCI at each dose level. This sub-set analysis will investigate if the combination of cryoablation and current active cancer treatment will lead to enhanced increases in percent of peripheral blood CD8⁺ T cell expression of PD-1 and Ki67 and/or CD8⁺ T cells displaying an activated effector-like phenotype.

5 Study Enrollment and Withdrawal

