6.1.2 Dose Escalation Protocol

A standard 3+3 dose escalation strategy will be used. The table below shows the doses that will be provided. Three participants will be initially enrolled at Level 1. If none of the first three participants at a given dose experiences dose-limiting toxicity (DLT), the dose will be escalated. If two or more of the first three participants experience DLT, the prior dose will be deemed the maximum tolerated dose (MTD) and the study will be terminated. If one of the first three participants experiences DLT, an additional three participants will be enrolled at the same dose. If among these six, only one experiences DLT, the dose will be terminated. If two or more of six experience DLT, the prior dose will be deemed the MTD and the study will be terminated. If the MTD is reached and only three participants have been treated at that dose, an additional three will be treated to ensure six subjects are treated at the MTD. DLT are defined in Section 4.1.1 (Primary Study Endpoints: Feasibility and Safety).

| Dose Level | Freeze Time (per site) | Thaw Time |
|------------|------------------------|---|
| Level 1 | 1 second | Will last until the probe separates from target tissue* |
| Level 2 | 2 seconds | Will last until the probe separates from target tissue* |
| Level 3 | 3 seconds | Will last until the probe separates from target tissue* |
| Level 4 | 5 seconds | Will last until the probe separates from target tissue* |
| Level 5 | 10 seconds | Will last until the probe separates from target tissue* |
| Level 6 | 20 seconds | Will last until the probe separates from target tissue* |

CONFIDENTIAL

| Level 7 | 30 seconds | Will last until the probe separates from target |
|---------|------------|---|
| | | tissue* |

6.1.3 **Procedures for Training of Clinicians on Procedural Intervention**

The NYU Interventional Pulmonary service has extensive experience using the flexible cryoprobe for debulking of central airway tumors. BCI will be performed by a board-certified, NYU Interventional Pulmonologist.

Only patients with the presence of a bronchus or airway path leading directly to the peripheral lung tumor will be eligible to undergo BCI. The peripheral tumor will also need to be identified by radial EBUS prior to performing BCI. If the peripheral tumor is unable to be identified by radial ultrasound within 20 minutes, then the patient will not be a candidate to undergo BCI.

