10.4.3 Analysis of the Primary Endpoint: Safety

Safety endpoints will be descriptive in nature, and any possible, probable, or definite adverse event will be counted only once for a given participant. Frequency and severity of all adverse events will be reported, both in the total study population and stratified by dose level.

Dose-limiting toxicities will be tabulated in the whole population and by dose level. Bleeding severity will be graded based on severity scale as described in Section 4.1.1 (Primary Study Endpoints: Feasibility and Safety). Pneumothoraces will be reported and described based on size, associated

CONFIDENTIAL

symptomatology and respiratory impairment, and need for chest tube placement. Length of time to perform BCI and length of time of fluoroscopy exposure during BCI will be reported in minutes. Other adverse events will be recorded and categorized as per the NCI Common Terminology Criteria for Adverse Events (CTCAE) (33).

The maximum tolerated dose (MTD) will be determined based on the dose escalation rules described below and in Section 6.1.1. The MTD is the dose at which fewer than 1 of 3 or at most 1 of 6 participants on that dose experience a DLT.

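### Dose level records freeze seconds per site but not cycle count or probe, and signed-rank tests within each level cannot answer the optimal-freeze-time question

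*Combined protocol and SAP*

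**What the plan says.** **Dose.** The Protocol Summary equates the MTD with freeze duration. The tables in 2.2.3 and 6.1.2 give seven levels: 1, 2, 3, 5, 10, 20 and 30 seconds, each per site.

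**Cycles.** Section 6.1.1 states: "For each one centimeter of the longest diameter, one freeze-thaw cycle will be performed". Sections 5.1 and 5.2 set no limit on tumor size. Section 2.2 words it differently, setting the cycles "with exact number based on tumor size and dose escalation protocol", although the dose tables vary freeze time only.

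**Probe.** The probe is 1.9 mm, but in 6.1.1 a "single-use flexible 1.1mm outer diameter cryoprobe will be used if robotic bronchoscopy is being performed". Neither probe is tied to a level.

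**Safety analysis.** Section 10.4.3 states: "Dose-limiting toxicities will be tabulated in the whole population and by dose level". Adverse events are handled the same way.

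**Immune analysis.** Section 10.4.4 tests paired pre/post changes with the Wilcoxon signed-rank test. Section 10.4.7 applies the same test at each dose level (item 1) and looks at active cancer treatment (item 2). Section 4.2.3 gives the purpose of the by-level analysis: "This sub-set analysis will investigate if there is an optimal freeze time duration for inducing anti-tumor immune responses". Section 10.4.1 sets significance at 0.05 without stating sidedness, and says the study is not powered for secondary outcomes.

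**The concern.** There are two gaps.

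First, two participants at the same level can differ in the number of sites frozen and in the probe used, and no planned table would show it. The protocol treats both factors as relevant. Section 2.1 (part II) counts a smaller probe diameter among the reasons to expect less bleeding than with percutaneous cryoablation, and grade 2 or 3 bleeding is a DLT. Section 2.2.1 describes the murine immune effect for animals given two cycles. If everyone treated at the MTD had the same probe, the plan would still report that MTD without qualification.

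Second, the search for an optimal freeze time is a comparison between levels. A signed-rank test inside one level asks only whether CD8+ values changed there. Seven such tests give seven separate answers and no comparison.

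**Working it through.** **1. The plan's own figure.** Section 10.5 gives escalation probabilities for one DLT rate p per level. The 3+3 rule gives P(escalate) = (1−p)³ + 3p(1−p)²·(1−p)³. For p = 10% to 70% this is 0.906, 0.709, 0.494, 0.309, 0.172, 0.082 and 0.032, which matches the printed 0.91 to 0.03. (At 80% the formula gives 0.0088 against a printed <0.001; that is a separate matter.)

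**2. What a within-level test can reach.** The smallest exact two-sided signed-rank p with n pairs is 2/2ⁿ.

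| n | smallest two-sided p |
|---|---|
| 3 | 0.25 |
| 4 | 0.125 |
| 5 | 0.0625 |
| 6 | 0.031 |

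A one-sided test at n = 3 gives 1/8 = 0.125. The normal approximation gives z = (6−3)/√3.5 = 1.60, so p = 0.11 two-sided and 0.054 one-sided. No version reaches 0.05.

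Most levels would have three. Seven levels of three use 21 participants; with the summary's maximum of 24, only one level could then be expanded to six. Pairs may be fewer still, because 7.1.2 takes no post-BCI blood from treated participants found not to have NSCLC.

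**3. What a pooled trend test can reach.** With only three levels of three, there are 9!/(3!·3!·3!) = 362,880/216 = 1,680 allocations of the ranked changes to levels. The smallest two-sided permutation p is 2/1,680 = 0.0012. This shows attainability, not power, but the test does address differences between levels.

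**4. Total freeze time.** Total seconds = seconds per site × cycles, with cycles taken as centimeters of longest diameter. Tumor sizes are assumed, because the documents give none.

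| Level (s per site) | 2 cm | 4 cm | 5 cm |
|---|---|---|---|
| 1 (1) | 2 | 4 | 5 |
| 2 (2) | 4 | 8 | 10 |
| 3 (3) | 6 | 12 | 15 |
| 4 (5) | 10 | 20 | 25 |
| 5 (10) | 20 | 40 | 50 |
| 6 (20) | 40 | 80 | 100 |
| 7 (30) | 60 | 120 | 150 |

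Steps between adjacent levels are 1.5- to 2-fold. Two adjacent levels overlap when the ratio of largest to smallest tumor exceeds the step.

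- 2–5 cm (ratio 2.5): all six adjacent pairs overlap. For example, 5 cm at Level 5 is 50 s and 2 cm at Level 6 is 40 s.
- 2–4 cm (ratio 2): three pairs overlap (Levels 2–3, 3–4 and 6–7) and three tie.
- Ratio below 1.5: no pair overlaps.

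**5. Why this could matter for escalation (illustration).** Assume an independent DLT risk r at each site, so the participant's rate is 1−(1−r)ᵏ for k cycles. Put that rate into the formula in step 1, with every participant at the level having the same k.

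| r | k = 2 | k = 5 | k = 7 |
|---|---|---|---|
| 3% | 0.96 | 0.83 | 0.73 |
| 5% | 0.91 | 0.65 | 0.49 |
| 10% | 0.73 | 0.29 | 0.15 |

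The documents give neither r nor evidence that risk accumulates by site.

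**The case against.** A reader might infer that dose level misstates exposure. The documents do not support that. Dose is defined as freeze time per site, one cycle per centimeter is a deliberate size-scaled rule, and a level reports the assigned dose correctly. Nothing in the protocol says that seconds summed over different sites are the dose.

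A reader might also infer that tumor-size mix will decide the MTD, or that the two probes carry different bleeding risks. The first needs the assumed per-site risk in step 5. The second goes beyond Section 2.1, which compares BCI with percutaneous cryoablation and does not compare 1.1 mm with 1.9 mm.

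It is tempting to replace level by cumulative seconds in the immune analysis. But cumulative seconds contain tumor size, so a correlation with them could not separate size from freezing, and 4.2.3 asks about freeze duration. That objection stands and shapes the fix.

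It is also fair that results are not reported by level alone. DLTs are pooled and tabulated by type, and immune change is tested pooled and in relation to active treatment. Tumor characteristics (10.4.5) and per-site thaw times (2.2.3) are already to be collected, and the by-level analysis is labeled exploratory. These points limit the seriousness. They do not supply a between-level comparison, and they do not put probe or cycles beside the DLTs.

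**Conclusion.** The concern holds as a gap in analysis and reporting; the dose definition itself is not in error. Level omits cycles and probe, and Section 10 uses neither. The optimal-freeze-time question is assigned to tests that do not compare levels and that cannot reach the plan's 0.05 in a three-participant level; at six the floor is 0.031, and only if all six pairs are available and all change in the same direction. These statements need no assumption. The overlap in total freeze time does: it runs from none to all six adjacent pairs, depending on the spread of tumor sizes. The effect of probe diameter on DLTs or immune response cannot be sized from the documents.

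**What to change.** Leave dosing and escalation as they are.

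- **10.4.7 item 1.** Replace the within-level tests with one exploratory rank correlation (trend test) of CD8+ change against per-site freeze seconds over all participants with paired samples. Name the post-BCI time point and the marker combination beforehand. Show cumulative freeze seconds only as a sensitivity analysis, alongside tumor diameter. Make per-level results descriptive.
- **10.4.3.** For each participant list tumor diameter, cycles delivered, cumulative freeze seconds and probe. Use cycles delivered, since no rule is given for fractions of a centimeter. Show DLTs by probe. Report the MTD with the number treated with each probe at that level, so that it is not claimed for a probe not used there.
- **2.2 against 6.1.1 and 6.1.2.** Reconcile the statement that cycle number also depends on the escalation protocol with the text and table that tie it to tumor size alone.

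The cost is a few table columns and one extra exploratory test. Cycles can be counted from the per-site thaw times and are needed anyway to judge completion under 4.2.1. Probe should be available from the procedure record. Counts by probe will be small and should be read descriptively.
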